4.1.1.2 Presentation

Patient dispositions (number and percentage) of subjects enrolled, subjects not randomised (incl. reasons), subjects randomised, subjects randomised and who did not receive treatment, subjects who started treatment, subjects who completed the treatment, subjects who discontinued treatment (incl. reasons), subjects included in the cough substudy, subjects who completed the study and subjects withdrawn from study (incl. reasons) will be presented in a summary table for each study intervention group and overall. A listing including all standardised disposition terms will also be provided for all discontinued subjects and subjects completing the study. Both the table and the listings will be based on the screened set.

To demonstrate balance in stratification factor categories (i.e. countries), the number and percentage of participants in each category will be summarised by study intervention group and overall focusing on the randomised set.

The recruitment per country and site will be provided based on the screened set, while the global/country situation study disruption will be summarised on the full analysis set.

The number and percentage of participants with one or more disruption due to COVID-19 pandemic will be presented by study intervention group considering the participants valid for the full analysis set. A listing of all the participants affected by COVID-19 related study disruption will be produced by unique patient number identifier, investigational site, and a description of how the individual's participation was altered. COVID-19 related study disruptions can be:

- Visit related (if visit is impacted by global/country situation, then contact mode will be specified);
- Study drug related (if study drug action taken (except "Drug Withdrawn") was impacted by global/country situation; study drug administration or location was impacted by global/country situation; who performed a study drug administration);

- Discontinuation of study drug due to COVID-19 pandemic (if study drug action taken "Drug Withdrawn" was impacted by global/country situation);
- Withdrawal from study (if primary reason for ending study is related to global/country situation).

Randomisation scheme and codes as well as participants receiving the various batch of investigational product will also be listed for all randomised participants.

4.1.2 Analysis Sets

4.1.2.1 Definitions and Derivations

The analysis populations used in the analysis have been described in Section 3.2.

4.1.2.2 Presentation

The number of participants belonging to each analysis population will be presented in a summary table for each study intervention group on the Screened set.

A listing of all participants excluded from any population will also be provided. The listing will include reason for exclusion from respective population and will be based on the screened set.

4.1.3 Protocol Deviations

4.1.3.1 Definitions and Derivations

The definition of IPD is available in Section 3.3.6. Deviations from the protocol will be assessed as important or non-important by blinded members of the study team before database hard lock and unblinding. A blind data review meeting will be held.

4.1.3.2 Presentation

The number and percentage of participants with at least one IPD, including COVID-19 related IPD, will be summarised following the PDP categories, for each study intervention group and overall.

All IPDs will also be listed for all participants included in the FAS population. All issues reported due to COVID-19 pandemic, regardless of whether the type of issue is considered a protocol deviation or not, will be listed separately.

4.1.4 Demographics

4.1.4.1 Definitions and Derivations

Demographics are collected pre-treatment as per schedule of activities (CSP Section 1.3). they include age, age group ($\geq 40 - < 65$; $\geq 65 - \leq 80$), sex, race, ethnic group, region and country. Age is the age at screening as reported in the eCRF.

4.1.4.2 Presentation

All demographics will be presented in summary tables for each study intervention group and overall. Age will be described as a continuous variable; all the other demographics (i.e., age group, gender, race, and ethnicity) will be summarised as categorical variables with the number and percentage of participants by categories.

All demographics will also be provided in listings.

The tables and the listings will be based on the FAS.

4.1.5 Baseline Characteristics

4.1.5.1 Definitions and Derivations

Patient characteristics are collected pre-treatment as per schedule of activities (CSP Section 1.3). They include height (cm) and weight (kg) at baseline.

Body Mass Index (BMI) (kg/m²) is calculated at baseline from the height (m) and weight (kg) as follows: BMI = weight / (height²). Only the baseline measurement for height, weight and BMI will be considered.

The lung function variables from spirometry collected at baseline/screening are: absolute and % predicted (as applicable) PEF, FEV1, FVC, FEV1/FVC, forced mid-expiratory flow (FEF25-75%), and forced inspiratory vital capacity. Screening spirometry data will be used for any subjects with missing baseline spirometry data.

For patients with missing Baseline spirometry results, screening results will be used, with ZephyrX results prioritised over Unify if both are available.

In case data issues for % predicted FEV1 and FVC are not resolved for database lock, any implausible values (i.e. <1% or >500%) will be set to missing, and consequently excluded from analysis.

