5.1 Inclusion Criteria

Participants are eligible to be included in the study only if all of the following criteria apply:

Age

1 Participant must be 40 to 80 years of age inclusive, at the time of signing the ICF.

Type of Participant and Disease Characteristics

- 2 Participants who have a confirmed primary diagnosis of moderate to severe COPD as per GOLD criteria (FEV1/FVC < 0.7, and post-BD FEV1 ≥ 25% predicted) (Global Initiative for Chronic Obstructive Lung Disease 2022).
- Participants who are current or ex-smokers with a tobacco history of ≥ 10 pack-years.

 Pack-years are calculated as average number of cigarettes per day × number of years / 20.

 For example, 1 pack-year = 20 cigarettes smoked per day for 1 year or 10 cigarettes per day for 2 years.
- 4 Participants must be deemed at high risk of exacerbations as defined by any one of the following:
 - (a) A documented history of ≥ 1 moderate or severe AECOPD requiring systemic corticosteroids and/or antibiotics for at least 3 days' duration (or 1 injection of depot formulation), or hospitalisation for reason of AECOPD in the 24 months prior to screening. A verbal history from the participant of AECOPD is not sufficient. Acceptable documentation is:

- Clinic visit or consultation (primary or specialist HCP) notes or emergency room/hospital records providing evidence of ≥ 1 moderate or severe AECOPD in the previous 24 months prior to enrolment
- Documented prescription of systemic corticosteroids of at least 3 days' duration (or 1 injection of depot formulation) and/or antibiotics for treatment of an AECOPD event. In participants with an established self-management plan, documented filling of a prescription to replace an above course of therapy will be considered as adequate
- Discharge summaries from a hospital, emergency room, or an urgent care facility indicating that a participant was hospitalised or treated with systemic corticosteroids or antibiotics for a COPD exacerbation, or
- (b) Frequent productive cough, defined as a positive response to both of the following questions:*
 - Over the past 3 months, I have coughed at least several days a week
 - Over the past 3 months, I have brought up phlegm (sputum) at least several days a week, or
- (c) Post-BD FEV1 < 50% predicted.

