2 CHANGES TO PROTOCOL PLANNED ANALYSES

- The Per-Protocol Set defined in the protocol will not be used for the analysis.
- The Cough subset will then be defined as a subset of the Full Analysis Set.
- The randomized Set is added to this analysis.
- The following biomarkers will not be delivered prior to DBL and will not be part of the CSR:
 - o Sputum parameters including differential cell counts, and markers of neutrophil activation and inflammation;
 - o neutrophil- related circulating biomarkers;
 - o Putative biomarkers of lung tissue destruction and COPD disease progression;
 - o nasal lining fluid biomarkers.
- Daily assessments of BCSS and Cough VAS will be analysed as 2-weekly means according to periods defined in Section 3.3.3.
- Laboratory safety analysis will be based on abnormality and not on treatment emergent change.
- Safety analysis will not use either the While on Treatment or Treatment policy estimand policy, and will simply include all on study data.
- Screening spirometry values will be used at Baseline if the Baseline results are missing. For % predicted FEV1 and FVC, implausible values due to data issues will be excluded from statistical analysis

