The study is powered using COPDCompEx, a composite endpoint used to estimate the magnitude of treatment effect on moderate and severe exacerbations of COPD. The time to first COPDCompEx event will be compared between AZD4831 QD vs placebo arms using a logrank test. A total of 194 first COPDCompEx events (estimated to require 203 participants per arm) will provide 80% power at the two-sided 10% level of statistical significance to detect a hazard ratio of 0.70 in the AZD4831 5 mg QD arm based on a 24-week first COPDCompEx event risk of 55% assumed in the placebo arm (constant over the course of the study). A screen failure rate of 40% is assumed, therefore approximately 677 participants will be screened to achieve the randomisation of 406 participants.

Cough Monitoring Substudy

A cough monitoring substudy will be performed alongside this study, where a subset of participants (maximum of 50 participants from each arm) from selected sites will be included. Twenty-four-hour cough frequency monitoring will be conducted at Visit SV3 (start of treatment) and Visit SV5 (after 12 weeks of treatment) using the VitaloJAK® Cough Monitor device. The main objective of the substudy is to explore the effect of AZD4831 compared with placebo on change in average 24-hour, awake, and sleeping cough frequency between baseline and Week 12. The substudy will also investigate whether average cough frequency is associated with lung function (e.g., PEF or FEV1), cough/COPD symptom scores (e.g., BCSS, CAT, and cough VAS) and sputum/blood biomarkers (e.g., MPO concentration).

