4.2.1.7 Subgroup Analyses

The subgroup analysis will be conducted for exploratory purposes.

The Cox proportional hazards model specified above would also be run separately with the "while on treatment" strategy for the following subgroups:

- Frequent Productive Cough (Yes; No)
- Gender (Male; Female)
- Age $(\ge 40 <65; \ge 65 \le 80)$
- Race (as collected in CRF)
- BMI (<18; ≥ 18 to <25; ≥ 25 to <30; ≥ 30)
- Geographic region (North America (Canada, United States of America), Eastern Europe (Bulgaria, Poland, Turkey), Western Europe (Denmark, Germany, Italy, Netherlands, Spain, United Kingdom), Rest of the world (Argentina, Mexico, South Africa).
- Baseline FEV1 as percent of predicted (<50%; ≥50%)
- Maintenance medications:
 - o ICS; no ICS
 - LABA/ICS; LABA/LAMA/ICS; LABA/LAMA
- Number of COPD exacerbations in last 24 months ($\langle 2; \geq 2 \rangle$)
- Type of site of recruitment (primary care site; specialist care site)
- Smoking status (Current smokers; Ex-smokers)
- MPO concentration at baseline (upper tertile; middle tertile; lower tertile)

The hazard ratio estimate from the Cox PH model will be provided with a 90% CI only for subgroup categories that contain at least 20% of the total participants.

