4.2.9.1 Definition

Data collected will include, but are not limited to, absolute and % predicted (as applicable) PEF, FEV1, FVC, FEV1/FVC, forced mid-expiratory flow (FEF25-75%), and inspiratory capacity. The following parameters will be included in the analysis PEF, FEV1, FVC, FEV1 and FVC % predicted, FEV1/FVC, forced mid-expiratory flow (FEF25-75%) and forced inspiratory vital capacity. At SV3 and SV5, face-to-face spirometry will be undertaken at the site, followed by virtual spirometry. At SV4 and SV7, virtual spirometry will be performed away from the study site prior to attendance at the site and then face-to-face spirometry will be performed subsequently once the participant has attended the site.

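### If % predicted FEV1 and FVC problems remain at database lock, the 1%–500% fallback keeps values that are not credible and deletes recoverable ones instead of recomputing them

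*SAP*

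**What the plan says.** SAP 4.1.5.1 (Baseline Characteristics, Definitions and Derivations) opens the rule with a condition: "In case data issues for % predicted FEV1 and FVC are not resolved for database lock". If that condition is met, "any implausible values (i.e. <1% or >500%) will be set to missing, and consequently excluded from analysis". SAP section 2 lists the change without limits: "implausible values due to data issues will be excluded from statistical analysis". The SAP amendment history dates the change to 25 September 2024 and marks it as not in line with the protocol. Neither section gives a narrower range, a check against the measured volume, or a recalculation.

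SAP 4.1.5.1 also substitutes screening spirometry where baseline spirometry is missing. It does not say whether a % predicted value that the rule has set to missing is then replaced in this way.

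Protocol 5.1, criterion 2, requires "FEV1/FVC < 0.7, and post-BD FEV1 ≥ 25% predicted" for entry.

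% predicted is used in three places:
- the lung-function tables at screening and baseline (SAP 4.1.5.2);
- the subgroups split at 50% of predicted FEV1, for the primary endpoint (SAP 4.2.1.7) and for FEV1 (SAP 4.2.3.7);
- the exploratory mixed model of spirometry, whose parameters include "FEV1 and FVC % predicted, FEV1/FVC, forced mid-expiratory flow (FEF25-75%) and forced inspiratory vital capacity" (SAP 4.2.9.1 and 4.2.9.4).

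**The concern.** The sponsor expected faulty % predicted values late in the study and wrote down one remedy for those still unresolved at lock. That remedy sorts values by size alone, and its limits are far outside what this population can produce. A faulty value between 1% and 500% is treated as a measurement. A value outside the limits is discarded even if the spirometry behind it was sound.

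% predicted is a derived quantity: the measured volume divided by a reference value. A fault in the derived field does not imply a fault in the measurement. Absolute FEV1 and FVC, height, age, sex and race are all collected (SAP 4.1.4.1 and 4.1.5.1), so the ingredients for a repair are largely at hand.

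At stake are the accuracy of the reported baseline severity, the placing of participants in the <50%/≥50% subgroups, and the exploratory model of % predicted.

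**Working it through.** **Inputs from the documents.** Retained range 1% to 500% (SAP 4.1.5.1); FEV1 entry floor 25% (Protocol 5.1); 203 participants per arm (SAP 3.3: "estimated to require 203 participants per arm").

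**Inputs not in the documents.** Neither document gives a mean or SD for % predicted. I assume a mean of 50% and an SD of 12 to 20 points.

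**The plan's own figure.** The only planned figure used here is the arm size.
- Events, Schoenfeld formula: 4 × (1.645 + 0.842)² / (ln 0.70)² = 194.4, against 194 stated.
- Risk under treatment: 1 − 0.45^0.70 = 42.8%. The average with 55% is 48.9%, and 194 / 0.489 ≈ 397 participants, against 406 stated.

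The two totals are about 2% apart, so 203 per arm is a fair basis.

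**Effect of one retained faulty value x on an arm.** With n − 1 sound values of mean m and SD s:
- shift in mean = (x − m) / n
- SD = √{[(n − 2)s² + ((n − 1)/n)(x − m)²] / (n − 1)}

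Example with n = 203, m = 50, s = 15, x = 400: [201 × 225 + (202/203) × 350²] / 202 = (45,225 + 121,897) / 202 = 827.3, so the SD is 28.8, or 1.92 times 15. The mean moves by 350 / 203 = 1.7 points.

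Ratio of the arm SD to its true value:

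| Retained value | True SD 12 | True SD 15 | True SD 20 |
|---|---|---|---|
| 200% | 1.33 | 1.22 | 1.13 |
| 300% | 1.77 | 1.54 | 1.33 |
| 400% | 2.28 | 1.92 | 1.58 |
| 500% | 2.81 | 2.33 | 1.87 |

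For a retained value of 1% or 5%, the ratio lies between 1.01 and 1.04 over the same SDs. Doubling the SD takes a value of about 346% (SD 12) or 420% (SD 15). For SD 20 it would take about 544%, which the rule would remove.

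**Subgroups.** This needs no assumed SD. A faulty baseline FEV1 from 50% to 500% is placed in the ≥50% group, and one from 1% to just under 50% in the <50% group, whatever the true value. Each faulty value moves at most one participant, and moves nobody if the true value lies on the same side of 50%.

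**Deleted values.** A true 45% stored as the fraction 0.45 is below 1% and is set to missing. Multiplying by 100, or recomputing from the measured FEV1, would recover it.

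**The case against.** The best defence is that the limits are a last resort. They apply only to problems not resolved by lock, and other controls come first: independent over-reading of the eligibility spirometry and real-time session checks (Protocol 8.2.3), automated over-reading (Protocol 6.1.1), and a blinded data review meeting before lock (Protocol 9.4.1). The tables also report median, quartiles, minimum and maximum, and the values are listed, so a 400% entry would be seen. All of this is true and limits the harm. Yet the rule exists for values that get past those steps, and for those it gives the wrong answer.

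Recomputation is also less simple than it looks. Neither document names a reference equation. Screening may use a site's own spirometer or the supplied ZephyrX device, while later visits use a different spirometer with UNIFY. The cause of the data problem is not stated. This stands, and the fix must therefore name an equation and cover all devices.

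The 25% floor applies to FEV1 at entry. It does not bound FVC or later visits, and it sets no upper limit. The argument against 400% rests on the obstructed population, not on that criterion.

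A reader might infer three stronger points that the documents do not support:
- **That borderline values are thrown away.** Deleted values are below 1% or above 500%, which are gross errors. The fair complaint is that some of them are recoverable.
- **That the SD ratio carries over to a between-arm confidence interval.** For SD 15 and one 400% value, √[(827.3 + 225) / 450] = 1.53. No planned analysis has that interval: baseline % predicted is only summarised, and the mixed model analyses change from baseline with baseline as a covariate.
- **That the main efficacy result is at risk.** The log-rank and Cox analyses and the secondary post-bronchodilator FEV1 model do not use % predicted.

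**Conclusion.** The point holds as a small, specific defect in a fallback rule. If it comes into force, values that are not credible in this population are analysed as real, and recoverable values are lost. The consequences are confined to descriptive tables, exploratory subgroups and one exploratory model.

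The SD figures assume 203 per arm, a mean of 50% and the SDs shown. A doubling is close to the worst case, and rises of 13–54% are what values of 200–300% produce for SD 20 to 15. At the low end the SD is hardly touched, so the harm there is a wrong subgroup or a reported minimum that contradicts the entry criterion. The documents do not say how many values are faulty, or whether any lie between 1% and 500%, so the actual effect cannot be estimated. The change is still worth making because it is cheap and protects a reported subgroup analysis of the primary endpoint.

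**What to change.** Replace the rule in SAP sections 2 and 4.1.5.1, before unblinding, so that it does the following:
- names one reference equation;
- where the % predicted field is affected by the unresolved problem, recomputes it for all records and all devices from the measured FEV1 or FVC with age, sex and height, and race if the equation needs it;
- sets % predicted to missing only when the measured volume is itself missing or invalid;
- derives the <50%/≥50% subgroup from the recomputed value;
- states that the rule also applies after baseline, and whether a baseline value set to missing is then replaced by the screening value.

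The cost is a short derivation program and a few lines of SAP text, with no new data. The drawback is that recomputed values may differ slightly from those the devices reported, so a participant near 50% could change subgroup. A footnote to the affected outputs should say which source was used.

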4.1.5.2 Presentation

All patient-specific characteristics will be presented in summary tables for each study intervention group and overall. Height, weight, and BMI will be summarised as a continuous variable. BMI categories (<18, ≥ 18 to <25, ≥ 25 to <30, ≥ 30 (kg/m²) will be summarised as a categorical variable.

Lung function parameters will be summarised in a separate table as continuous variables.

Lung function parameters (FEV1, FVC, FEV1/FVC and FEV1% predicted) at screening will be summarised in a separate table as continuous variables.

All patient-specific characteristics will also be provided in listings.

The tables and the listings will be based on the FAS population.

4.1.6 Disease Characteristics

4.1.6.1 Definitions and Derivations

The patient's COPD history will be collected and will include questions related to the:

- COPD first diagnosed date
- First appearance of COPD symptoms date
- GOLD Classification
- Occurrence of previous admission to ICU for COPD in past 24 months
- Required mechanical ventilation for COPD
- Occurrence of Cough at least several days/week over past 3 months

Brought up phlegm at least several days/week over past 3 months

4.1.6.2 Presentation

The following variables will be summarised by intervention group and overall for FAS:

- Time since COPD diagnosis (years)
- Time COPD symptoms started (years)
- GOLD Classification
- Occurrence of previous admission to ICU for COPD in past 24 months
- Number of moderate and severe exacerbation within 24 months prior enrolment
- Frequent productive cough
- Use of disease-related medications (ICS + LABA + LAMA or ICS + LABA or LABA + LAMA)

4.1.7 Medical History and Concomitant Disease

4.1.7.1 Definitions and Derivations

Complete medical and surgical history will be collected as per SoA (CSP Section 1.3). Medical history will be coded in Medical Dictionary for Regulatory Activities (MedDRA) version 24.1 or higher.

4.1.7.2 Presentation

Medical history will be presented in summary tables as number and percentage of participants by System Organ Class (SOC) and Preferred Term (PT) for each study intervention group and overall. Participants with multiple events in the same SOC/PT will be counted only once

in that SOC/PT. Participants with events in more than one SOC/PT will be counted once in each of those SOC/PT. Tables will be sorted alphabetically by SOC and PT. The tables will be based on the FAS population.

4.1.8 Prior and Concomitant Medications

4.1.8.1 Definitions and Derivations

Any prior and concomitant medication(s), including herbal preparations, taken during the study will be recorded in the eCRF. The WHO-DD March 2022 B3 Global or higher will be used to classify medications by WHO ATC classification of ingredients. The imputation method described in Section 3.3.1.4 will be used in case of medication stop date partially missing. Completely missing stop date will not be imputed. Completely missing or partially missing concomitant medication start dates will not be imputed.

After the end date imputation, the medications will be classified as either prior or concomitant (but not both) according to its stop date:

- Prior medication is defined as any medication with a stop date prior to the first dose of IP (exclusive).
- Concomitant medication is defined as any medication with a stop date on or after the first dose of study drug, or any medication taken prior to study drug and that is ongoing.

Medications with completely missing stop date are classified as concomitant.

Disallowed medications will include medications defined as prohibited according to CSP Section 6.5. They will be defined following a physician review (prior to database lock) of the unique combinations of ATC code classifications and generic terms captured and detailed in the Integrated Data Review Plan.

COVID-19 vaccine information will be recorded and summarised as part of concomitant medication. For reporting purposes, COVID-19 vaccines will be selected using ATC code J07BX.

